9.2 KEY SECONDARY EFFICACY PARAMETER

The key secondary endpoint is the change from baseline to Week 6 in the CGI-S score.

To test the secondary hypotheses that each dose of cariprazine is superior to placebo in the reduction of CGI-S score after 6 weeks of treatment, the change from baseline in CGI-S score will be analyzed using the MMRM approach similar to the one used for the primary analysis. A sensitivity analysis will also be performed using ANCOVA (with LOCF imputation) as used for the analysis of primary endpoint.

To control the overall familywise type I error rate at the 0.025 level (one-sided), a truncated Hochberg will be used for the primary endpoint, and the regular Hochberg procedure for the key secondary endpoint. The truncation parameter will be set to $\gamma = 0.9$ (Dmitrienko 2011).

The cariprazine dose groups will be labeled as Dose 1 (1.5 mg) and Dose 2 (3.0 mg).

The null hypotheses can be grouped into two families:

- (i) Family 1 includes the null hypotheses H_1 and H_2 for the primary endpoint:

H_1 denotes the null hypothesis of the difference in mean change from baseline in MADRS at Week 6 between cariprazine Dose 1 and placebo is ≥ 0 .

H_2 denotes the null hypothesis of the difference in mean change from baseline in MADRS at Week 6 between cariprazine Dose 2 and placebo is ≥ 0 .

- (ii) Family 2 includes the null hypotheses H_3 and H_4 for the key secondary endpoint:

H_3 denotes the null hypotheses of the difference in mean change from baseline in CGI-S at Week 6 between cariprazine Dose 1 and placebo is ≥ 0 .

H_4 denotes the null hypotheses of the difference in mean change from baseline in CGI-S at Week 6 between cariprazine Dose 2 and placebo is ≥ 0 .

The gatekeeping procedure utilizes the following decision rules:

- (i) Step 1. The null hypotheses in Family 1 are tested using the truncated Hochberg procedure at the full α level. Let $p_{(1)} < p_{(2)}$ denote the ordered p-values in Family 1 and let $H_{(1)}$ and $H_{(2)}$ denote the associated null hypotheses. The truncated Hochberg procedure rejects both $H_{(1)}$ and $H_{(2)}$ if $p_{(2)} \leq \alpha(1 + \gamma)/2$ or it rejects only $H_{(1)}$ if $p_{(1)} \leq \alpha/2$ and $p_{(2)} > \alpha(1 + \gamma)/2$.
- (ii) Step 2. The null hypotheses in Family 2 are tested as follows:
- (i) The null hypotheses are tested using the regular Hochberg procedure at the full α level if both $H_{(1)}$ and $H_{(2)}$ are rejected. Let $p_{(3)} < p_{(4)}$ denote the ordered p-values in Family 2 and let $H_{(3)}$ and $H_{(4)}$ denote the associated null hypotheses. The Hochberg procedure rejects both $H_{(3)}$ and $H_{(4)}$ if $p_{(4)} \leq \alpha$ or it rejects only $H_{(3)}$ if $p_{(3)} \leq \alpha/2$ and $p_{(4)} > \alpha$.
- (ii) The null hypothesis logically related to $H_{(1)}$ is tested at $\alpha(1 - \gamma)/2$ if $H_{(1)}$ is rejected and $H_{(2)}$ is not rejected.
- (iii) Step 3. If only one null hypothesis is rejected in Family 1 and only one null hypothesis is rejected in Family 2, the remaining null hypothesis in Family 1 is re-tested at the full α level. If this null hypothesis is rejected, the associated null hypothesis in Family 2 is tested at the full α level.

9.3 ADDITIONAL EFFICACY PARAMETER(S)

Additional efficacy parameters will include the following at postbaseline visits described in [Table 3-2](#):

- Change from baseline in MADRS total score at Weeks 1, 2, 4
- Change from baseline in the CGI-S score at Weeks 1, 2, 4
- CGI-I score at Weeks 1, 2, 4, 6

- CGI-I response (CGI-I score ≤ 2) at Weeks 1, 2, 4, 6
- MADRS response ($\geq 50\%$ reduction from baseline in MADRS total score) at Weeks 1, 2, 4, 6
- MADRS remission (MADRS total score ≤ 10) at Weeks 1, 2, 4, 6
- Change from baseline in the HAMD-17 total score at Week 6
- Change from baseline in the HAM-A total score at Week 2, 6
- HAM-A response ($\geq 50\%$ reduction from baseline in HAM-A total score) at Weeks 2, 6
- HAM-A remission (HAM-A total score ≤ 7) at Weeks 2, 6
- Change from baseline in MADRS individual item scores at Weeks 1, 2, 4, 6
- Change from baseline in HAM-A individual item scores at Weeks 2, 6

Additional quantitative efficacy parameters will be analyzed in the following way:

Analysis of CGI-I score, change from baseline in HAM-A total score, change from baseline in MADRS and HAM-A individual item scores, and change from baseline in CGI-S will be performed using a similar MMRM to that used for the primary analysis. Baseline CGI-S score will be used as a covariate for the analysis of CGI-I score. In addition, these parameters will be analyzed using ANCOVA (with LOCF imputation) as used for the analysis of primary efficacy parameters.

Change from baseline in HAMD-17 total score will be analyzed based on ANCOVA model using observed cases, with treatment group, pooled country, and ADT failure category (per CRF) as factors and baseline HAMD-17 total score as a covariate for between-treatment-group comparisons at Week 6.

Additional categorical efficacy parameters will be analyzed in the following way:

Rates for categorical parameters (response and remission) will be reported by treatment group and by visit; a logistic regression model (with LOCF imputation) will be used to model the probability of a response or the probability of a remission as a function of a treatment group, pooled country, ADT failure category (per CRF) and the corresponding baseline score (CGI-S for the analysis of the CGI-I response) as explanatory variables.

10.0 **SAFETY ANALYSES**

The safety analysis will be performed using the safety population for the double-blind treatment period and safety follow-up period. The double-blind treatment period starts with the first dose of double-blind investigational product and ends with the last scheduled assessment at Visit 6 (Week 6) or early termination (before Week 6). The safety follow-up period starts the day after the last scheduled assessment at Visit 6 (or early termination) and ends with the last safety follow-up visit. The safety parameters will include adverse events (AEs), clinical laboratory parameters, vital signs, electrocardiogram (ECG) parameters, EPS scales, the C-SSRS and the YMRS. For each safety parameter, the last assessment made before the first dose of double-blind investigational product will be used as the baseline for all analyses of that safety parameter. The summarization will be by treatment group for both double-blind and safety follow-up periods. Continuous variables will be summarized by number of participants and mean, SD, median, minimum, and maximum values. Categorical variables will be summarized by number and percentage of participants.

10.1 **ADVERSE EVENTS**

Adverse events will be coded by system organ class and preferred term using the *Medical Dictionary for Regulatory Activities*, version 24.0.

An adverse event (AE) will be considered a treatment-emergent adverse event (TEAE) if the AE began or worsened (increased in severity or became serious) on or after the first dose of DB investigational product. Per case report form instructions, a new AE record will be created with a new AE onset date for any AE that worsens. Therefore, TEAEs can simply be identified as those AEs with recorded onset date (and time, if known) on or after the date of the first dose of study intervention.

An AE will be considered a TESAE if it is a TEAE that additionally meets any SAE criterion.

For the DB treatment period, the number and percentage of participants reporting TEAEs in each treatment group will be tabulated by system organ class and preferred term; by system organ class, preferred term, and severity; and by system organ class, preferred term, and relationship to the IP. If more than 1 AE is coded to the same preferred term for the same participant, the participant will be counted only once for that preferred term using the most severe and most related occurrence for the summarization by severity and by relationship to the IP.

The distribution of TEAEs by severity and relationship to the IP will be summarized by treatment group.

The TEAEs during the safety follow-up period will be summarized by body system, preferred term, and treatment group for the safety population.

An AE that occurs more than 30 days after the date of the last dose of DB IP or occurs after the last safety follow-up visit (whichever comes last) will not be summarized except for AEs related to reported pregnancies. AEs associated with pregnancies reported in the protocol-required timeframe up to approximately 12 weeks following the last dose of DB IP will be summarized.

The number and percentage of participants with common ($\geq 2\%$ of participants in any treatment group) TEAEs, will be summarized by preferred term and treatment group for the double-blind period.

Summary tables will be provided for participants with TESAEs and participants with TEAEs leading to discontinuation if these occurred in 5 or more participants. The number and percentage of participants with TESAEs will be summarized for both the double-blind and safety follow-up periods.

Listings will be presented for participants with SAEs, participants with AEs leading to discontinuation, and participants who die (if any). All participants with SAEs, including SAEs reported during the screening period and the safety follow-up period, and participants discontinuing because of AEs occurring before the start of DB IP will be included in these listings.

The number and percentage of participants reporting TEAEs of ocular events of special interest during the double-blind treatment period will be summarized. A listing of all reported ocular events of special interest will be provided.

The number and percentage of participants with EPS TEAEs, EPS treatment-emergent SAEs, and the number and percentage of participants with EPS TEAEs leading to premature discontinuation during the double-blind treatment period will be summarized for the double-blind treatment period.

For EPS AEs, the preferred terms include:

Akathisia, Restlessness, Dystonia cluster (Dystonia, Myoclonus, Oculogyric crisis, Oromandibular dystonia, Tongue spasm, Trismus, Torticollis), Parkinsonism cluster (Akinesia, Bradykinesia, Cogwheel rigidity, Drooling, Dyskinesia, Extrapyrmidal disorder, Hypokinesia, Reduced facial expression, Muscle rigidity, Muscle tightness, Parkinsonism, Salivary hypersecretion, Tremor), Musculoskeletal stiffness, and Tardive dyskinesia.

For EPS AEs excluding Akathisia/Restlessness, the preferred terms include all the terms listed above except Akathisia and Restlessness.

Any EPS TEAEs including Akathisia/Restlessness, any EPS TEAEs excluding Akathisia/Restlessness, and any TEAEs of Akathisia/Restlessness will also be summarized.

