Evaluate SAFER Score Qualification ^g		X					
Modified ATRQ	X						
HAMD-17	X	X				X	
YMRS	X	X				X	
MADRS	X	X	X	X	X	X	
CGI-S	X	X	X	X	X	X	
CGI-I			X	X	X	X	

Study Period	Screening	Baseline	Double-blind Treatment				Safety Follow-up
Visit	1	2	3	4	5	6/ET	7
Study Week	Up to -2^k	0	1	2	4	6^{a,b}	10
Study Day	Up to -14^k	1	8	15	29	43	71
Visit Windows		(within 14 days of start of screening procedures) ^k	± 3 Days	± 3 Days	± 3 Days	± 3 Days	± 3 Days
HAM-A		X		X		X	
SF-12		X				X	
BARS/AIMS/SAS		X	X	X	X	X	
C-SSRS	X	X	X	X	X	X	X
Adverse Events	X	X	X	X	X	X	X
Concomitant Medications	X	X	X	X	X	X	X
Dispense IP		X	X	X	X		
Drug Return and Compliance			X	X	X	X	
ADT Compliance		X	X	X	X	X	
Pharmacogenetic Consent ^h	X			X			
Pharmacogenetic Sample ⁱ				X			
Pharmacokinetic Sample ^j				X	X	X	

Note: After completion of Visit 6/ET, patients will be treated at the discretion of the investigator or designee.

ADT = antidepressant therapy; AIMS = Abnormal Involuntary Movement Scale; ATRQ = Antidepressant Treatment Response Questionnaire; BARS = Barnes Akathisia Rating Scale; CGI-I = Clinical Global Impressions—Improvement; CGI-S = Clinical Global Impressions—Severity; C-SSRS = Columbia—Suicide Severity Rating Scale; ET = early termination; HAM-A = Hamilton Anxiety Rating Scale; HAMD-17 = Hamilton Depression Rating Scale—17 items; IP = investigational product; MADRS = Montgomery-Åsberg Depression Rating Scale; SAS = Simpson-Angus Scale; SF-12 = Short Form-12 v2 Health Survey; YMRS = Young Mania Rating Scale.

^a Performed for all patients, including those prematurely discontinued after randomization (Visit 2).

^b Clinical findings upon termination must be followed until the condition returns to prestudy status or can be explained as unrelated to investigational product. If necessary, an additional follow-up visit should be scheduled.

^c Verified Clinical Trials database check to be performed, where applicable.

^d Clinical laboratory tests include hematology, serum chemistry, urinalysis (including urine myoglobin in patients with creatine phosphokinase levels > 1000 U/L or as clinically indicated for any rise in creatine phosphokinase levels or as necessitated by symptoms), as well as serum pregnancy test in women of childbearing potential.

^e Urine drug screen, blood alcohol concentration (by Breathalyzer), and serum pregnancy test can be repeated at random at request of investigator.

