7.3.2 Other Efficacy Analyses

Additional quantitative efficacy parameters will be analyzed in the following way:

Analysis of CGI-I score, change from baseline in HAMD-17 total score, change from baseline in HAM-A total score, and change from baseline in CGI-S will be performed using a similar MMRM to that used for the primary analysis. Baseline CGI-S score will be used as a covariate for the analysis of change in CGI-I score. In addition, these parameters will be analyzed using ANCOVA (with LOCF imputation) as used for the analysis of primary efficacy parameters.

Additional categorical efficacy parameters will be analyzed in the following way:

Rates for categorical parameters (response and remission) will be reported by treatment group and by visit; a logistic regression model (with LOCF imputation) will be used to model the probability of a response or the probability of a remission as a function of a treatment group and the corresponding baseline score (CGI-S for the analysis of the CGI-I response) as explanatory variables.

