8.4.3 Double-blind Treatment Period (Visits 3 to 6/ET)

The following procedures will be carried out during the DB treatment period at every visit except as noted:

- Review concomitant medications and assess ADT compliance
- Collect IP blister cards, perform drug accountability and assess IP compliance
- Assess MADRS, CGI-S, CGI-I, and C-SSRS; HAM-A (Visits 4 and 6/ET only), YMRS (Visit 6/ET only) and HAMD-17 (Visit 6/ET only)
- Evaluate EPS (AIMS/BARS/SAS)
- Administer SF-12 (Visit 6/ET only)
- Collect vital signs measurements (including weight)
- Collect waist circumference measurement (Visit 6/ET only)

- Review and assess AEs and SAEs
- Collect blood sample for serum pregnancy test for women of childbearing potential (Visit 6/ET only)
- Collect blood samples for clinical laboratory determinations (Visit 6/ET only)
- Collect blood for PK evaluation (any time during Visits 4, 5 and 6/ET)
- If not already obtained previously, obtain consent for and collect blood for the pharmacogenetic sample. A single sample can be obtained at any time between Visit 2 and Visit 6/ET, inclusive
- Perform ECG (Visit 6/ET only)
- Perform physical examination (Visit 6/ET only)
- Access IWRS to dispense IP (Visit 3 through Visit 5), and register patient completing Visit 6/ET

Note: After completion of Visit 6/ET, patients will receive treatment for their MDD as deemed necessary by the Investigator or designee.

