Dosing compliance for the background ADT during a specified period is defined as the dose actually taken by a participant during that period divided by the dose expected to be taken during the same period multiplied by 100. Descriptive statistics for ADT compliance will be presented for each ADT and overall by the double-blind investigational product treatment group for the period from the first dose of DB IP actually taken to the last dose of DB IP actually taken for the Safety Population.

9.0 **EFFICACY ANALYSES**

All efficacy analyses will be based on the mITT population. Baseline for efficacy is defined as the last non-missing efficacy assessment before the date of the first dose of DB IP. All statistical tests will be conducted at the $\alpha=0.05$ (2-sided) level for main effects. All confidence intervals (CIs) will be 2-sided 95% CIs, unless stated otherwise.

For efficacy analyses in which country is a factor, a *small country* will be defined as a country with fewer than 2 participants in at least one treatment group in the mITT Population. Small countries will be pooled to form pseudo-countries so that each treatment group includes at least 2 mITT participants within the country. Countries will be ranked on number of participants that are part of the mITT Population and lowest ranked countries will be pooled (sequentially, i.e., a new ranking is made after each step) until the smallest pooled country has reached at least 2 participants in each treatment group.

To compare with historic studies, some analyses based on the imputed data using the last-observation-carried-forward (LOCF) approach, will be presented for all efficacy parameters. Only the postbaseline total score of a parameter will be imputed; individual item scores will not be carried forward. The baseline value will be carried forward only for the intermittent missing values immediately after baseline. If all the postbaseline values are missing, the baseline value will not be carried forward.

9.1 **PRIMARY EFFICACY PARAMETER**

The primary estimand is provided below through specification of the population, the variable, the handling of intercurrent events, and the population-level summary.

Population

The target population are participants with MDD who have had an inadequate response to antidepressant therapy in the current episode and who satisfy the inclusion and exclusion criteria as specified in the protocol.

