10.5.3 Suicidality Assessment

The number and percentage of patients with suicidal ideation or suicidal behavior as recorded on the C-SSRS will be summarized by treatment group. The distribution of responses for most severe suicidal ideation and most severe suicidal behavior during the patient's lifetime, during the DB treatment period, and during the safety follow-up period will also be presented by treatment group for the safety population. Supportive listings will be provided and will include the patient identification number, study center number, lifetime history, and postbaseline values. Intensity of suicidal ideation, suicidal behavior type, and lethality of suicidal behavior will also be included in these listings. A listing of all AEs occurring in patients who have suicidal ideation or suicidal behavior will also be provided.

11.0 **HEALTH OUTCOMES ANALYSES**

The SF-12 will be administered at Visit 2 and Visit 6/ET.

Analysis of change from baseline in the PCS-12 and MCS-12 score at Week 6 will be analyzed using the ANCOVA (based on observed cases) that has treatment group, pooled country, ADT failure category (per CRF) as factors and the baseline value as the covariate.

The detailed algorithms for derivation of the PCS-12 and MCS-12 score are presented in Section [15.2.1](#).

12.0 **INTERIM ANALYSIS**

No interim analysis is planned for this study.

13.0 **DETERMINATION OF SAMPLE SIZE**

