15.0 DATA HANDLING CONVENTIONS

15.1 VISIT TIME WINDOWS

Table 15-1 presents the visits assigned for efficacy and safety analyses and the corresponding range of treatment days (window) during which an actual visit may occur.

Table 15-1 Efficacy and Safety Analysis Visit Definitions

Analysis Phase	Derived Visit	Scheduled Visit Day ^a	Window
Pretreatment	Baseline	Day 1	Days ≤ 1
Double-blind Treatment	Week 1	Day 8	Days [2, 11]
	Week 2	Day 15	Days [12, 21]
	Week 4	Day 29	Days [22, 35]
	Week 6	Day 43	Days ≥ 36 and within Double-blind Treatment Period
	End of Double-Blind Treatment Period ^b	Final double-blind treatment visit (expected Day 43) or ET visit during the double-blind treatment period	Final non-missing assessment during the double-blind treatment period
Safety Follow-up	Week 10	Day 71	day of final double-blind or ET visit during the double-blind treatment period $+1 \leq \text{Days} \leq \text{last visit}$

a Relative to the date of the first dose of double-blind investigational product. Day 1 = the date of the first dose of double-blind investigational product.

b Presented in analysis tables for safety parameters, including but not limited to electrocardiograms, clinical laboratory values, and vital signs.

ET = early termination.

If the visit date is on or after the date of the first dose of double-blind investigational product, the study day is calculated by visit date – date of the first dose of double-blind investigational product + 1. If the visit date is before the date of the first dose of double-blind investigational product, the study day is calculated by visit date – date of the first dose of double-blind investigational product. Therefore, a negative day indicates a day before the start of the double-blind investigational product.

If a participant has 2 or more visits within the same window, the last visit with a non-missing value will be used for analysis.

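### The only Week 6 analysis specified for HAMD-17 and SF-12 is an observed-case ANCOVA, which omits patients who terminate before Day 36; for HAMD-17 the protocol's LOCF analysis was dropped without being listed as a change

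*SAP*

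**What the plan says.** **Collection.** Protocol 8.4.3 schedules "HAMD-17 (Visit 6/ET only" during double-blind treatment, and SF-12 likewise. Visit 7 collects neither. Footnote a of protocol Table 1 says of this visit: "Performed for all patients, including those prematurely discontinued after randomization (Visit 2". Protocol 8.8 defines the final assessment of a withdrawn patient as the full Visit 6/ET evaluation.

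**Windows.** SAP Table 15-1 assigns visits by study day: Days 2-11 are Week 1, Days 12-21 Week 2, Days 22-35 Week 4. Week 6 is "Days ≥ 36 and within Double-blind Treatment Period". The end-of-double-blind derived visit, which would pick up an earlier ET value, is designated for safety tables.

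**Analysis.** For HAMD-17, SAP 9.3 says: "Change from baseline in HAMD-17 total score will be analyzed based on ANCOVA model using observed cases", compared at Week 6. For PCS-12 and MCS-12, SAP 11.0 says the change at Week 6 "will be analyzed using the ANCOVA (based on observed cases". The factors are treatment, pooled country and ADT failure category, with baseline as covariate. Neither section gives a second analysis.

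**LOCF.** Protocol 7.3.2 names HAMD-17 among the parameters analysed by MMRM and adds: "In addition, these parameters will be analyzed using ANCOVA (with LOCF imputation) as used for the analysis of primary efficacy parameters". SAP 9.0 says that some LOCF analyses "will be presented for all efficacy parameters". SAP 9.3 attaches LOCF to the MMRM endpoints and to response and remission, but not to HAMD-17. Appendix III records the move from MMRM to ANCOVA for HAMD-17. SAP 17.0 does not mention HAMD-17.

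**The concern.** With one scheduled postbaseline value, an observed-case ANCOVA is a complete-case analysis. It is unbiased only if having a Week 6 value depends on nothing beyond treatment, country, ADT failure category and baseline. The primary MMRM assumes less: under its missing-at-random assumption, dropout may also depend on the MADRS scores at Weeks 1, 2 and 4. A patient who leaves because of a poor Week 2 score is covered by the MADRS model but not by the HAMD-17 or SF-12 model.

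If the arms lose patients for different reasons, these endpoints can therefore disagree with the MADRS result purely because of who remains. The texts on LOCF also leave it open whether a second HAMD-17 analysis will exist.

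**Working it through.** **1. The plan's own figure.** The documents give no power for HAMD-17 or SF-12, so the check is on the MADRS inputs: 250 per arm, effect 0.286 SD, within-person correlation 0.58, dropout 15% (protocol 7.7, SAP 13.0).
- Effective n = 250 × (0.85 + 0.15 × 0.58²) = 225.1 per arm.
- Noncentrality = 0.286 × √(225.1/2) = 3.03.
- Regular Hochberg, two comparisons sharing placebo: 84.1% for each dose and 91.2% for at least one, against the protocol's 84% and 90%.
- Truncated Hochberg (0.9, no re-testing): 83.7% and 91.1%, against the SAP's 83% and 90%.

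The stated figures reproduce to within two points.

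**2. Patients left out.** 250 × 0.15 = 37.5 per arm; 750 × 0.15 = 112.5 in all; 250 − 37.5 = 212.5 per arm remain. These are upper limits on the exclusions, because ET values on Day 36 or later stay in Week 6. For assumed dropout of 5% to 25% the limit is 12.5 to 62.5 per arm.

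**3. Direction of bias.** Let g be how much worse dropouts would have scored than completers (assumed equal in both arms), and dA and dP the dropout proportions on active and placebo. Ignoring covariates, the completer difference minus the all-patient difference is −(dA − dP) × g.
- dA = 20%, dP = 10%, g = 2 to 6 points (all assumed): −0.2 to −0.6 points, favouring active.
- Proportions reversed: +0.2 to +0.6 points, against active.
- Equal dropout: 0.

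The direction is not fixed in advance.

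**4. Size for HAMD-17, by simulation.** From the plan: 250 per arm, 0.58, 0.286 SD, dropout near 15%. Assumed: exchangeable correlation over visits and a HAMD-17 to MADRS correlation of 0.85, so the true HAMD-17 effect is about 0.286 × 0.85 = 0.243 SD. Results with baseline adjustment, as SAP 9.3 specifies:

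| Dropout mechanism (assumed) | Bias of observed-case effect |
|---|---|
| Placebo follows poor scores, cariprazine random; dropout about 15-18% | 14-23% too small |
| The same at 15% per arm, moderate / strong selection | 16% / 24% too small |
| Equal selection in both arms | about 0-2% |

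Within-arm imputation from the MADRS history removed the bias: 0.242 against a full-data 0.241 SD with asymmetric dropout, and 0.240 against 0.241 SD with symmetric dropout.

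**5. LOCF in the same kind of simulation.** With asymmetric dropout LOCF gave 0.281 against 0.241 SD: (0.281 − 0.241)/0.241 = 17% too large. With symmetric dropout it gave 0.231, no real gain on the observed-case 0.229.

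**6. Text comparison.** Protocol 7.3.2 includes LOCF for HAMD-17, SAP 9.0 implies it, SAP 9.3 omits it and SAP 17.0 is silent. For SF-12, protocol 7.4.2 never promised LOCF, and SAP 17.0 does list the change of model factors.

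**The case against.** The strongest reply is that little is at stake and part is already covered. Both are additional endpoints outside the type I error procedure. SAP 9.0's general sentence can be read as still promising LOCF for HAMD-17. Appendix III discloses the change of model, and with one scheduled postbaseline visit the protocol's MMRM was already close to an observed-case ANCOVA, so the lead analysis did not become more selective. All of that stands. It does not settle what LOCF analysis HAMD-17 gets, because SAP 9.3 specifies none, and it does not weaken the missing-data assumption.

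For SF-12 the reply is stronger. SAP 15.2.1 gives a 4-week recall, so an ET value before about Day 29 partly describes time before treatment. Not counting it as Week 6 is defensible; what remains is the selection of patients.

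A reader might infer more than the documents support:
- *That every dropout is lost.* ET values on Day 36 or later are kept, and patients with no postbaseline MADRS are outside the mITT population and so outside the primary analysis too.
- *That the effect shrinks by a third or more.* Omitting the baseline covariate gave losses of 30% (moderate selection) and 40% (strong selection); the covariate SAP 9.3 specifies cut these to 16% and 24%. The HAMD-17 entry cut-off of 22 could weaken that adjustment somewhat.
- *That HAM-A has the same gap.* HAM-A also has an LOCF ANCOVA in SAP 9.3, and under SAP 15.2 an early ET value can be carried forward into it. Only the HAM-A MMRM misses ET values falling in the Week 1 or Week 4 window.
- *That restoring LOCF cures the problem.* It was itself biased under asymmetric dropout.

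**Conclusion.** The point holds in a limited form. HAMD-17, PCS-12 and MCS-12 are compared at Week 6 only among patients with a value on Day 36 or later, leaving out at most about 37 of 250 per arm at 15% dropout. For HAMD-17 the likely consequence ranges from negligible, if selection is alike in the arms, to an effect about 15-25% too small, if only placebo dropout follows poor scores. That range rests on assumed dropout mechanisms and an assumed 0.85 correlation with MADRS; other mechanisms could move the bias either way. No size is claimed for SF-12. Separately, SAP 9.3 departs from protocol 7.3.2 and conflicts with SAP 9.0 on LOCF for HAMD-17, and SAP 17.0 does not say so. The primary and key secondary analyses are untouched, so this should be corrected but does not threaten the trial's main conclusion.

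**What to change.** - **SAP 9.3:** add a multiple imputation of the Week 6 HAMD-17 score under MAR within each treatment arm. Predictors are baseline and all on-treatment MADRS and CGI-S scores, including those from the ET visit, followed by the same ANCOVA. Report it beside the observed-case ANCOVA.
- **SAP 11.0:** do the same for PCS-12 and MCS-12 as a sensitivity analysis.
- **Predictors to avoid:** do not use the HAMD-17 or SF-12 ET value. By design it is never observed together with a Week 6 value, so their association cannot be estimated.
- **LOCF:** reconcile protocol 7.3.2 and SAP 9.0 with SAP 9.3 for HAMD-17. If the LOCF ANCOVA is kept, label it as being for comparison with historic studies only.
- **SAP 17.0:** list the change of HAMD-17 method.

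The cost is SAP wording and one extra imputation program, with no new data, visits or patients. The added analyses rely on the MAR assumption already made for the primary endpoint.
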